### **2.3.2.2 Hemorrhagic Stroke**

Defined as an acute symptomatic focal or global cerebral dysfunction caused by a nontraumatic intraparenchymal, intraventricular, or subarachnoid hemorrhage; or asymptomatic neuroimaging-positivity, including greater than three cerebral microbleeds found with GRE-sequencing and/or CT hyperintensities

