### 2.3.2 Stroke/TIA Subtype Classification

#### 2.3.2.1 Ischemic Stroke

Defined as an acute symptomatic focal cerebral or retinal dysfunction caused by an infarction of central nervous system tissue.

1. a. Acute infarcts are classified as small, medium or large based on size of the largest ischemic lesion:
  - a. small = lesion in the anterior or posterior circulation <1.5 cm.
  - b. medium = equal to or greater than 1.5cm but less than a complete territory infarct lesion in a cortical superficial branch of the anterior cerebral artery (ACA), middle cerebral artery (MCA), posterior cerebral artery (PCA), or in a branch of MCA or PCA, or lesion in internal border-zone territories.
  - c. large posterior = lesion involving complete PCA territory, or lesion of cerebellum 1.5 cm or larger or any lesion of the brain stem.

- d. large anterior = lesion involving complete ACA or MCA territory, or lesion involving >1 artery territory
  - e. All classifications are based of the measurement of the largest lesion size with preferred sequencing to be GRE on MRI (*but all effort should be used to maintain the same modality of sequencing and magnet strength used at baseline*)
- 2.Subacute/chronic or 'old' infarcts (i.e. more than 2 weeks) are noted but not classified.
- 3.Transient Ischemic Attack (TIA)  
defined as an acute symptomatic focal cerebral, spinal, or retinal dysfunction in which symptoms resolve (typically in less than 1 day) without acute damage on neuroimaging.

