#### **3.2 Primary Objective**

In patients with atrial fibrillation with recent cerebral ischemic symptoms (0-48 hours), to evaluate whether the treatment regimen with Apixaban (Three subgroups: TIA: day 0-3; small stroke: day 3-5; medium stroke: day 7-9) compared with standard of care treatment regimen with warfarin (Three subgroups: TIA: day 7±5; Small or medium stroke: day 14±5) reduces the composite endpoint of fatal stroke, recurrent ischemic stroke or TIA at 30 and 180 days. (See figure 1)

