### **7 STUDY ENDPOINTS AND EVALUATIONS**

#### **7.1 Primary Endpoint**

Endpoint data will start at randomization up to 180 days. These composite endpoints include:

- Fatal stroke
- Recurrent Ischemic stroke
- New hemorrhagic stroke

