## 7.2 Secondary Endpoints

- Any intracranial bleeds assessed by MRI/CT scan at day 14 and EOS or at outcome event.
- Any major bleeds defined as clinically overt bleeding that was accompanied by one or more of the following: a decrease in hemoglobin of 2 g/dL or more; a transfusion of 2 or more units of packed red blood cells; bleeding that occurred in at least one of the following critical sites: intracranial, intraspinal, intraocular, pericardial, intra-articular, intramuscular with compartment syndrome, retroperitoneal; or bleeding that was fatal. Intracranial hemorrhage included intracerebral (hemorrhagic stroke), subarachnoid, and subdural bleeds.

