## 7.5 Efficacy and Safety Evaluations (see also schedule of events)

### 7.5.1 Diagnostic Tests, Scales, Measures, etc.

*MRI w/o contrast (GRE sequencing preferred but all effort should be used to maintain the same modality of sequencing and magnet strength from baseline or CT w/o contrast –*

Will be performed, along with the NIHSS, to measure the size of ischemic stroke at screening. It will also be used for follow-up assessments to indicate any early hemorrhagic transformation or micro-embolic strokes. Patients who are unable to have a MRI due to contraindication (i.e. implantable pacemaker) will have be allowed to use CT with the NIHSS.

- TIA- will have no ischemic changes
- Acute infarcts are classified as small, medium or large based on size of the largest ischemic lesion:
  - small = lesion in the anterior or posterior circulation <1.5 cm.
  - medium = equal to or greater than 1.5cm but less than a complete territory infarct lesion in a cortical superficial branch of the anterior cerebral artery (ACA), middle cerebral artery (MCA), posterior cerebral artery (PCA), or in a branch of MCA or PCA, or lesion in internal border-zone territories.
  - large posterior = lesion involving complete PCA territory, or lesion of cerebellum 1.5 cm or larger or any lesion of the brain stem.
  - large anterior = lesion involving complete ACA or MCA territory, or lesion involving >1 artery territory
- All classifications are based of the measurement of the largest lesion size.

*TEE-*

Will be obtained or scheduled prior to discharge on all patients or will be scheduled as part of their evaluation for potential cardiac sources of emboli. In addition to imaging specifically of left atrium thrombus; measurements will be obtained for left atrial size, left atrium appendage, velocity, left ventricle size and function and other significant myocardial or valvular heart disease.

*Carotid ultrasound-*

Will be performed on all patients to rule out ipsilateral carotid disease during the screening visit.

*Laboratory evaluations-*

Will be obtained from all patients at screening, day 30, day 90 and day 180. Additional lab measurements for the warfarin group will be obtained monthly and at unscheduled visits if warranted by the warfarin dosing protocol.

*Event Monitor-*

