#### **8.1.2 Efficacy Analysis/Primary Aim**

For the main outcomes, the proportion of patients with any primary outcome (fatal stroke, recurrent ischemic stroke, transient ischemic attack) will be computed along with the 95% confidence interval for the differences in treatment arms.

The primary outcome is defined as any component of the composite primary outcome occurred within 30 and 180 days or otherwise had adequate follow-up. Logistic regression models will be fitted with the primary outcome as the dependent variable and the SUBGROUP: (1) Apixaban TIA: day 0-3; (2). Apixaban small stroke: day 3-5; (3). Apixaban medium stroke: day 7-9; (4) warfarin TIA: day 7±5; (5) warfarin small stroke: day 14±5; (6) warfarin medium stroke: day 14±5 as the primary independent variable. The overall treatment effect will be assessed by the ESTIMATE and LSMEANS of all the Apixaban groups to all the warfarin groups. Comparison between individual subgroups will be assessed by constructing different ESTIMATE. For example, (1) Apixaban TIA versus (5) warfarin Small stroke: day 14±5. These analyses will be implemented by using SAS 9.2 PROC LOGISTIC which has the ESTIMATE and the LSMEANS statements for the group comparisons. P<0.05 is used for the overall treatment effects. All other subsequent subgroup testing will be adjusted for multiple comparisons by using PROC PLM.

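### Under the section 7.1 composite, a symptom-free bleed on a scheduled scan is a primary event and a symptom-free new infarct is not; this reaches the primary result only if 7.1 governs

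*Combined protocol and SAP*

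**What the plan says.** **Definitions.** Section 2.3.2.1 describes ischemic stroke as follows: "Defined as an acute symptomatic focal cerebral or retinal dysfunction caused by an infarction of central nervous system tissue". It offers no route through imaging alone. TIA in the same section also needs symptoms, and is an event "in which symptoms resolve (typically in less than 1 day) without acute damage on neuroimaging". Section 2.3.2.2 starts from symptomatic hemorrhage and then adds a second route: "or asymptomatic neuroimaging-positivity, including greater than three cerebral microbleeds found with GRE-sequencing and/or CT hyperintensities".

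**Composite.** Section 7.1 lists fatal stroke, recurrent ischemic stroke and "New hemorrhagic stroke". The primary objective in 3.2 asks whether the apixaban regimen "reduces the composite endpoint of fatal stroke, recurrent ischemic stroke or TIA at 30 and 180 days". Section 8.1.2 analyses that same set, with TIA and without hemorrhagic stroke. Section 8.1.3 takes intracranial hemorrhage as a separate safety outcome.

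**Scans.** Section 5.5 schedules MRI (CT where MRI is contraindicated) for all patients at day 14 and at end of study or early withdrawal. Section 7.5.1 says of this imaging: "It will also be used for follow-up assessments to indicate any early hemorrhagic transformation or micro-embolic strokes". Section 7.2 has as a secondary endpoint "Any intracranial bleeds assessed by MRI/CT scan at day 14 and EOS or at outcome event".

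**Adjudication.** Under section 2.3, the stroke adjudication committee knows the treatment arm.

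**The concern.** If 7.1 is the endpoint, its components are found in different ways. Ischemic stroke needs a clinical event. Hemorrhagic stroke can be found on a routine scan in a patient who has noticed nothing. The scans are meant to look for both kinds of lesion, but only one kind can become a primary event without symptoms.

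The hypothesis in 3.1 keeps the two questions apart: fewer recurrent ischemic strokes, without a significant increase in intracranial hemorrhage. A composite that takes in silent bleeds mixes them. Silent bleeds at equal rates in both arms pull the risk ratio towards 1. At unequal rates they can move the result either way, for reasons that have nothing to do with stroke prevention.

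Two features of the trial make unequal counts possible. The day 14 scan falls at a different point of anticoagulant exposure in each arm, and the adjudicators know the arm.

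**Working it through.** **1. What a scan finding becomes under each statement of the composite**

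| Finding | 7.1 | 3.2 and 8.1.2 | 8.1.3 |
|---|---|---|---|
| Symptom-free hemorrhage meeting 2.3.2.2, new since entry | primary event | not an event | safety event if intracranial hemorrhage |
| Symptom-free new infarct | not an event | not an event | not an event |
| Transient symptoms with acute damage on imaging | can become ischemic stroke, a primary event | primary event, as stroke instead of TIA | not an event |

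The first two rows are the asymmetry, and it exists only in the 7.1 column. The third row shows that a scan can still add an infarct event when symptoms were present, by moving a TIA (not in 7.1) to ischemic stroke (in 7.1).

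**2. Exposure at the day 14 scan**

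The scan window is day 11 to 17 (14 ± 3). The latest planned apixaban start is day 9 (medium stroke), so almost all apixaban patients will have started. Warfarin after a small or medium stroke starts on day 14 ± 5, that is day 9 to 19, so some of these patients will be scanned before their first dose. Scan-only bleeds may therefore be uneven by arm. The documents do not settle the direction: apixaban exposure begins earlier, while the table in 1.1 reports fewer intracranial bleeds per year on apixaban than on warfarin in the pivotal trial (0.33% v 0.80%).

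**3. The plan's own power figure**

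Section 8.1.5 gives 80% power for a control/experimental risk ratio of 2.30, with 20% control risk, 50 per arm and two-sided alpha 0.05. I used the normal approximation with pooled variance:

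power = Φ[(d − 1.96 × SE0) / SE1], where SE0 = √(2p̄(1 − p̄)/n) and SE1 = √([p1(1 − p1) + p2(1 − p2)]/n).

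With p1 = 0.20 and p2 = 0.20/2.30 = 0.087: d = 0.113, p̄ = 0.1435, SE0 = 0.0701 and SE1 = 0.0692. Power = Φ(−0.352) = 36% (42% with 60 per arm). The stated 80% is reproduced only if the risk rises from 20% to 46% (79.9%), the inverse of the labelled ratio. That is a separate matter. Here 36% is simply the starting point.

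**4. Adding silent bleeds**

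Let h be the share of patients with a silent hemorrhagic finding, independent of clinical events. The documents give no value, so h is an assumption shown over a range. Each risk becomes p′ = p + (1 − p)h. For h = 5%: control 0.20 + 0.80 × 0.05 = 24.0%; experimental 0.087 + 0.913 × 0.05 = 13.3%; ratio 1.81. With equal h the absolute difference shrinks only by the factor (1 − h).

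| h, both arms | Ratio | Difference, points | Power, 50 per arm | Power, 60 per arm |
|---|---|---|---|---|
| 0 | 2.30 | 11.3 | 36% | 42% |
| 1% | 2.16 | 11.2 | 34% | 40% |
| 2% | 2.05 | 11.1 | 32% | 38% |
| 5% | 1.81 | 10.7 | 28% | 33% |
| 10% | 1.57 | 10.2 | 23% | 26% |
| 15% | 1.43 | 9.6 | 19% | 22% |

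**5. Unequal rates**

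With 10% on apixaban and 5% on warfarin, the risks are 24.0% for warfarin and 0.087 + 0.913 × 0.10 = 17.8% for apixaban. The ratio is 1.35, the difference 6.2 points, and power 11% (50 per arm) or 13% (60 per arm). Reversed, with 5% on apixaban and 10% on warfarin, the risks are 28.0% and 13.3%, and the difference widens from 11.3 to 14.7 points.

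**The case against.** The strongest objection is about reach. The hypothesis, the primary objective and the analysed outcome in 8.1.2 all leave hemorrhagic stroke out, and 8.1.3 already handles intracranial hemorrhage on its own. Under the analysis as written, a silent bleed adds nothing to the primary result. This stands, and the point is conditional for that reason. It does not dispose of the point, because 7.1 is the section that defines the primary endpoint and it names hemorrhagic stroke.

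Second, a broad count of bleeding is a defensible cautious choice in a pilot of early anticoagulation. That is fair, but the plan gives no such rationale for the primary composite, and 7.2 and 8.1.3 already provide the broad count.

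Third, silent-bleed rates may be low. Patients with more than three microbleeds, or with hemorrhage on CT, are excluded at entry, and 7.1 counts only new hemorrhagic stroke. At 1% to 2% in both arms the loss is small, as the table shows. On the other side, up to three microbleeds are allowed at entry and 2.3.2.2 uses an absolute count, so one more can cross the threshold.

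A reader might infer more than the documents support:

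- *That scans can never add infarcts.* This holds only for symptom-free infarcts.
- *That silent bleeds will cancel a real benefit.* Such a case can be built: clinical risks of 10% v 15% (apixaban v warfarin) with silent bleeds of 12% v 6% give 1 − 0.90 × 0.88 = 20.8% against 1 − 0.85 × 0.94 = 20.1%. It depends on assuming twice as many silent bleeds on apixaban. With 6% in both arms the composite reads 15.4% v 20.1%. In any case, 60 per arm gives only about 13% power for 10% v 15% before any silent bleed is added.
- *That counting a bleed in both 7.1 and 7.2 is an error.* Overlap between a composite and a safety endpoint is ordinary, and symptomatic bleeds would still overlap after the fix.

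**Conclusion.** The asymmetry is plain on the text of 2.3.2.1, 2.3.2.2 and 7.1. It affects the primary result only if the 7.1 list governs; if 3.2 and 8.1.2 govern, it does not.

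If 7.1 governs, equal silent-bleed rates cause a dilution that is slight at 1% to 2% and material on the ratio scale from about 5% upward (2.30 to 1.81 or lower). The absolute difference changes much less. An imbalance between arms is the larger risk, and exposure at the day 14 scan together with unblinded adjudication makes one possible. Neither its direction nor its size can be derived from the documents.

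The figures rest on the 20% control risk and the 2.30 ratio in 8.1.5, on assumed silent-bleed rates, and on independence of silent bleeds from clinical events. Most of the gap between 36% and the stated 80% power has nothing to do with this point.

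**What to change.** Reconcile 7.1 with 3.2 and 8.1.2 so that one list defines the primary composite. If hemorrhagic stroke stays in it, state in 7.1 that only symptomatic or fatal hemorrhagic stroke counts, in line with the symptom requirement in 2.3.2.1. Keep imaging-only hemorrhage in the 7.2 secondary endpoint and the 8.1.3 safety analysis, so that no safety information is lost.

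Optionally, tabulate imaging-only new infarcts by arm as a descriptive result. This needs a rule for reading each follow-up scan against baseline, because 2.3.2.1 notes but does not classify infarcts more than two weeks old, and some patients will have CT.

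The main change costs definition wording and no new procedures. The downside is fewer composite events. The optional table adds some reading effort.

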#### 4.3.2 Exclusion Criteria

1. Hemorrhagic stroke
2. Large ischemic stroke
3. History of major bleeding within the last 6 months from time of subject enrollment (e.g. GI bleed).
4. History of intracranial bleed
  - a. Traumatic intracranial bleed within one year of randomization. (Traumatic ICH greater than one year of randomization is not an exclusion).
5. Current or history of bleeding disorders (e.g. blood dyscrasias)
6. Blood Pressure of 180/100 mmHg on hypertensive therapy day of randomization per PI discretion.
7. Current illicit drug use and/or chronic alcohol use per PI discretion.
8. Severe liver disease (AST/ALT 2x upper limit).
9. Patients with kidney disease meeting criteria to take 2.5 mg twice daily who are taking strong dual inhibitors of CYP3A4 and P-glycoprotein (e.g. ketoconazole, itraconazole, ritonavir, clarithromycin) .
10. Any other suspected etiology for stroke (e.g. ipsilateral carotid disease).
11. Greater than 3 Cerebral Micro-bleeds (CMB) on gradient recovery echo (GRE) or evidence of intracranial hemorrhage on CT at time of randomization. (SWI sequencing may be used if GRE sequencing is not obtainable)
12. Therapeutically anti-coagulated at time of admission (INR at admission greater than 2.0 on warfarin or took two consecutive doses of NOAC).
13. Absolute indication for use of warfarin only.( e.g. Mechanical Valve)
14. Absolute indication for anticoagulation prior to randomization window. (e.g. DVT)
15. Hemoglobin less than 9 gm/dl and/or platelet count less than 100 K/uL.
16. Requires dual antiplatelet therapy.

17. Daily use of NSAIDS
18. Pregnancy or lactation.
19. Any use of an investigational product within the past 30 days.
20. Prisoners or subjects who are involuntarily incarcerated.
21. Subjects who are compulsorily detained for treatment of either a psychiatric or physical (eg, infectious disease) illness.
22. Concurrent participation in another clinical study where use of an investigational product is used

Subjects that do not meet all of the enrollment criteria may not be enrolled. Any violations of these criteria will be reported in accordance with IRB Policies and Procedures.

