#### For individual patients

In the event of a Grade 3 or higher adverse event attributable to treatment with APIXABAN and not related to the underlying disease, administration of APIXABAN will be suspended in the patient to allow analysis and determination whether to continue the treatment, alter dosing regimen or to exclude the patient from further participation in the study; if there is any increase in cerebral microbleeds (CMB) at day 14, in either arm, all study medication will be suspended until a repeat MRI is performed 48 hours from day 14 MRI. Study medication will be restarted in clinically stable individuals. In subjects who have a CT scan at day 14 and have a asymptomatic intracranial hemorrhage, all study medication will be suspended until a repeat CT is performed at 48 hours from the day 14 scan. Sstudy medication will be restarted in clinically stable individuals. If subjects experience any symptomatic hemorrhagic transformation in either arm, study medication will be suspended. All subjects will continued to be followed up monthly either by phone or clinic contact until the end of study.

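### The imaging limb of hemorrhagic stroke uses a total count above three microbleeds while entry allows up to three, so event status depends partly on lesions present before randomization

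*Combined protocol and SAP*

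**What the plan says.** Section 2.3.2.2 gives two routes to a hemorrhagic stroke. One is a symptomatic, nontraumatic bleed. The other needs no symptoms: "asymptomatic neuroimaging-positivity, including greater than three cerebral microbleeds found with GRE-sequencing and/or CT hyperintensities". It does not say that the microbleeds must be new or compared with an earlier scan.

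Exclusion 11 in section 4.3.2 bars "Greater than 3 Cerebral Micro-bleeds (CMB) on gradient recovery echo (GRE) or evidence of intracranial hemorrhage on CT at time of randomization", so counts of 0 to 3 are admitted. It adds that "SWI sequencing may be used if GRE sequencing is not obtainable". Section 5.5 schedules MRI (or CT) at day 14 and at end of study or early withdrawal.

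The definition can feed two outcomes:

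- **Composite.** Section 7.1 lists "New hemorrhagic stroke" as a component. Section 8.1.2, however, analyzes "any primary outcome (fatal stroke, recurrent ischemic stroke, transient ischemic attack", and the objective in 3.2 names the same three components. Hemorrhagic stroke is in neither.
- **Safety.** Section 7.2 lists "Any intracranial bleeds assessed by MRI/CT scan at day 14 and EOS or at outcome event", and 8.1.3 analyzes intracranial hemorrhage as a yes/no outcome. Section 7.2 describes intracranial hemorrhage as including hemorrhagic stroke and gives no microbleed rule of its own.

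Elsewhere the protocol does compare counts over time. The suspension rule in 7.5.2 applies "if there is any increase in cerebral microbleeds (CMB) at day 14, in either arm".

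**The concern.** An outcome event should reflect what happens after randomization. Here the entry limit and the event threshold are the same number, and the threshold applies to the total count. Lesions the patient brought into the trial are therefore carried into the outcome. Two patients with identical new bleeding can be classified differently, and a patient with less new bleeding can be an event when one with more is not.

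Every patient scanned by MRI at day 14 and end of study is exposed to this limb, with or without symptoms. Randomization is stratified by TIA, small stroke and medium stroke only (5.2, 8.1.6), so baseline microbleed count is not balanced by design. Whether the word *New* in 7.1 means new lesions is left to an adjudication committee that, under section 2.3, is not blinded to treatment arm.

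**Working it through.** The plan gives no figure for this point, so there is none to reproduce. The defect follows from the two cut-offs alone.

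**Step 1: new microbleeds needed.** An event needs a total above three, that is, at least 4 (2.3.2.2). The permitted baseline count b is 0, 1, 2 or 3 (exclusion 11). New lesions needed = 4 − b:

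- b = 0: 4 − 0 = 4
- b = 1: 4 − 1 = 3
- b = 2: 4 − 2 = 2
- b = 3: 4 − 3 = 1

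**Step 2: ordering.** Patient A goes from 3 to 4: one new lesion, event. Patient B goes from 0 to 3: three new lesions, no event. The classification reverses the order of new bleeding.

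**Step 3: does other text remove the carry-over?**

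- *New* in 7.1 qualifies the stroke. No section says that baseline lesions are subtracted, and a count that moves from 3 to 4 is newly above the threshold.
- 7.5.2 uses an increase in count, but for suspension of study drug and not for the endpoint.
- 2.3.2.1 and 7.5.1 ask for every effort to keep the same sequencing as at baseline. That protects comparability of scans; it does not change what is counted.

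**Step 4: illustration of the dependence on baseline.** The documents give no rate of new microbleeds. *Assume* that new lesions per patient, X, follow a Poisson distribution with mean m between 0.05 and 0.5. Then P(event given b) = P(X ≥ 4 − b). For b = 3 and m = 0.1 this is 1 − exp(−0.1) = 9.5%.

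| Baseline | New needed | m = 0.05 | m = 0.1 | m = 0.25 | m = 0.5 |
|---|---|---|---|---|---|
| 0 | 4 | <0.0001% | 0.0004% | 0.013% | 0.18% |
| 1 | 3 | 0.002% | 0.016% | 0.22% | 1.4% |
| 2 | 2 | 0.12% | 0.47% | 2.6% | 9.0% |
| 3 | 1 | 4.9% | 9.5% | 22.1% | 39.3% |

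At any given rate of new bleeding, the chance of being an event is governed largely by the baseline count.

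**Step 5: weight of one event.** With 120 patients randomized 1:1 there are 60 per arm, and one event moves an arm's risk by 1/60 = 1.7 percentage points.

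**The case against.** The strongest reply is that this is a coherent, if coarse, threshold-crossing rule. Because entry and endpoint share a cut-off, nobody is an event at baseline, and on a consistent sequence every microbleed event needs at least one new lesion. That is true. It does not answer the ordering problem in step 2, because the same new bleeding still counts for one patient and not for another.

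Four stronger readings are tempting, and the documents do not support them:

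- **One new microbleed makes an event.** This holds only for patients who enter with exactly three. Those with 0, 1 or 2 need four, three or two.
- **The primary result is contaminated.** That follows from 7.1 but not from 3.2 or 8.1.2, which leave hemorrhagic stroke out. As the analysis is written, the firmer route is the intracranial hemorrhage outcome.
- **A change of sequence alone will create events.** It could, since SWI is allowed at entry while the endpoint names GRE and CT. But 2.3.2.1 and 7.5.1 ask for the same sequencing throughout, so the protocol addresses this risk. What it lacks is a rule for scans where that effort fails.
- **The arms will differ spuriously by 2 to 3 points.** Suppose 12 patients enter with two or three microbleeds. A split of 8:4 or worse in either direction has probability 2 × 794/4096 = 0.39. If a third to a half of them crossed the threshold, the four-patient excess would give 4 × 1/3 ÷ 60 = 2.2 to 4 × 1/2 ÷ 60 = 3.3 points. Every input is assumed. With an even mix of twos and threes and the step 4 probabilities, crossing is (0.47% + 9.5%)/2 = 5.0% at m = 0.1 and (9.0% + 39.3%)/2 = 24.2% at m = 0.5. The same split then gives 0.3 to 1.6 points.

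Two further points stand against calling this bias. Randomization balances baseline microbleeds on average, so a chance difference has expectation zero. Section 8.1.1 also brings unbalanced covariates into the regression, and 8.1.4 examines other variables that differ at enrollment. Microbleeds are not named in either, but they are not ruled out.

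**Conclusion.** The point holds as a defect of definition. Read as written, section 2.3.2.2 makes an imaging-only hemorrhagic stroke depend partly on microbleeds present before randomization: 4, 3, 2 or 1 new lesions are needed for baseline counts of 0, 1, 2 or 3. This needs no assumption beyond the two stated cut-offs and the plain reading that the count is a total.

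It affects the intracranial hemorrhage outcome, through the inclusion of hemorrhagic stroke in 7.2, and the composite as listed in 7.1. The disagreement of 7.1 with 3.2 and 8.1.2 over TIA and hemorrhagic stroke is a separate matter to be reconciled.

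The consequence is misclassification of new bleeding, added noise, and exposure to chance imbalance in an unstratified baseline factor. The documents do not support a claim of systematic bias between arms. The number of patients affected and the effect on the arm difference cannot be calculated without a baseline microbleed distribution and a rate of new microbleeds. The percentages and point differences above only illustrate the mechanism.

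**What to change.** In 2.3.2.2, define the microbleed limb by lesions new since the baseline scan, with one fixed number of new lesions that applies whatever the baseline count. The sponsor should set that number before any endpoint is adjudicated and reconcile the wording with exclusion 11, 7.1 and 7.5.2.

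The choice of number matters, and the documents do not settle it. Under the step 4 assumptions, requiring more than three new lesions gives every patient an event probability of at most 0.18%, which nearly empties this limb and still leaves 0 to 3 as a non-event. Requiring one new lesion gives 4.9% to 39.3%. These figures show the trade-off; they do not recommend a number.

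Also:

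- Record the baseline count and the sequence on the adjudication form.
- Flag follow-up scans read on a different sequence or modality and handle them in a sensitivity analysis. Leaving them unclassified would create missing safety outcomes.
- Report symptomatic hemorrhage separately from imaging-only microbleed events, in both the composite and the hemorrhage outcome.

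The cost is a reworded definition, two form fields, one sensitivity analysis and a split in the tables. No extra scan is needed. The downside is that imaging-only events may become rarer, and a few scans with a changed sequence will remain uncertain.
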